4.2.2 Concomitant Medications

a) Corticosteroids: Patients receiving systemic corticosteroids who have not been on a stable or decreasing dose of corticosteroid for at least 7 days prior to enrollment are not eligible. If used to modify **immune adverse events** related to prior therapy, ≥ 14 days must have elapsed since last dose of systemic corticosteroid (See Section [4.1.6.1.d](#)). Note: patients who are using topical or inhaled corticosteroids are eligible.

b) Investigational Drugs: Patients who are currently receiving another investigational drug are not eligible.

c) Anti-cancer Agents: Patients who are currently receiving other anti-cancer agents are not eligible [except leukemia patients receiving hydroxyurea, which may be continued until 24 hours prior to start of protocol therapy].

d) Anti-GVHD agents post-transplant:

Patients who are receiving cyclosporine, tacrolimus or other agents to prevent graft-versus-host disease post bone marrow transplant are not eligible for this trial.

4.2.3 Infection: Patients who have an uncontrolled infection are not eligible.

4.2.4 Patients who have received a prior solid organ transplantation are not eligible.

4.2.5 Patients who in the opinion of the investigator may not be able to comply with the safety monitoring requirements of the study are not eligible.

5.0 TREATMENT PROGRAM

5.1 Overview of Treatment Plan

Day 1	Day 15	Day 28
VX15/2503 IV	VX15/2503 IV	End of Cycle/Evaluation

VX15/2503 will be administered intravenously over 60 minutes on Days 1 and 15 of a 28 day cycle. Patients should be monitored for signs and symptoms of infusion reactions during the drug infusion and for 4 hours after completion of post-infusion flush (e.g., monitor vital signs every 15 minutes during VX15/2503 infusion and every 30 minutes thereafter). Precautions for anaphylaxis should be observed during VX15/2503 administration. Emergency resuscitation equipment and medications should be present for immediate use in the immediate area where patients are receiving their infusions. If a patient develops a \geq Grade 2 infusion related reaction, the infusion should be stopped and standard institutional guidelines for management of infusion reactions should be followed. Note: If the initial dose is well tolerated subsequent doses will required patients to be monitored for 1 hour after completion of post-infusion flush.

See Section [6.2.3](#) for management and dose modification guidelines for infusion related reactions. If there is no evidence of an infusion related reaction during the initial 2 infusions of VX15/2503, then no observation period is required for subsequent treatment cycles. In the event an infusion related reaction occurs thereafter, the four-hour observation period should be reinstated.

A cycle of therapy is considered to be 28 days. A cycle may be repeated for a total of 13 cycles, up to a total duration of therapy of approximately 12 months. As some of the correlatives require same-day shipping (see [Section 8.5](#)), caution should be paid to the day of the week therapy should start and drug infusion should occur so that correlative samples are able to be sent out for analysis without delay.

Drug doses should be adjusted based on weight measured within 7 days prior to the beginning of each cycle.

Update: With the release of Amendment #2A, the dose confirmation portion of the study is complete. Given this, Part B will be open to patients \geq 12 months and \leq 30 years of age with relapsed and refractory osteosarcoma once the initial 6 adult patients complete toxicity assessments per [Section 11.6](#).

5.2 Criteria for Starting Subsequent Cycles

A cycle may be repeated every 28 days if the patient has at least stable disease and has again met laboratory parameters as defined in the eligibility section, [Section 4.0](#), and is eligible to continue agent administration per the requirements in [Section 6.0](#).

5.3 Dose Confirmation Schema (Completed)

5.3.1 Inter-Patient Escalation

The starting dose will be 20 mg/kg (dose level 1)

Dose Level	Dose (mg/kg)
------------	--------------

THIS PROTOCOL IS FOR RESEARCH PURPOSES ONLY, SEE PAGE 1 FOR USAGE POLICY

-1	10
1*	20

* Starting Dose Level

If the MTD has been exceeded at the first dose level, then the subsequent cohort of patients will be treated at a dose of 10 mg/kg (dose level -1). If dose level -1 is not well tolerated, further de-escalation will not occur. The study will be closed to accrual.

Update: The RP2D was determined to be 20 mg/kg.

5.3.2 Intra-Patient Escalation

Intra-patient dose escalation is not allowed.

5.4 **PK Expansion Cohort and Part B**

VX15/2503 will be administered intravenously over 60 minutes on Days 1 and 15 of a 28 day cycle at the RP2D of 20 mg/kg.

5.5 **Grading of Adverse Events**

Adverse events (toxicities) will be graded according to the NCI Common Terminology Criteria for Adverse Events (CTCAE) version 5.0. All appropriate treatment areas should have access to a copy of the CTCAE version 5.0. A copy of the CTCAE version 5.0 can be downloaded from the CTEP website (http://ctep.cancer.gov/protocolDevelopment/electronic_applications/ctc.htm). Any suspected or confirmed dose-limiting toxicity should be reported immediately (within 24 hours) to the Study Chair.

5.6 **Definition of Dose-Limiting Toxicity (DLT)**

DLT will be defined as any of the following events that are possibly, probably or definitely attributable to protocol therapy. The DLT observation period for the purposes of dose-confirmation will be the first cycle of therapy.

Dose limiting hematological and non-hematological toxicities are defined differently.

5.6.1 Non-hematological dose-limiting toxicity

a) Any Grade 3 or greater non-hematological toxicity attributable to protocol therapy with the specific exclusion of:

- Grade 3 nausea and vomiting < 3 days duration
- Grade 3 liver enzyme elevation, including ALT, that returns to Grade \leq 1 or baseline prior to the time for the next treatment cycle. See [Appendix III](#) for values that represent thresholds between CTCAE grades. Note: For the purposes of this study the ULN for ALT is defined as 45 U/L.
- Grade 3 fever
- Grade 3 infection
- Grade 3 hypophosphatemia, hypokalemia, hypocalcemia or hypomagnesemia responsive to supplementation.

b) Non-hematological toxicity that causes a delay of \geq 14 days between treatment

THIS PROTOCOL IS FOR RESEARCH PURPOSES ONLY, SEE PAGE 1 FOR USAGE POLICY
cycles.

- c) Note: Allergic reactions that necessitate discontinuation of study drug will not be considered a dose-limiting toxicity.

5.6.2 Hematological dose limiting toxicity

- a) In patients evaluable for hematological toxicity (see [section 4.1.7.1](#)), hematological dose limiting toxicity is defined as:

- Day 15:
 - o Grade 4 neutropenia or Grade 3 thrombocytopenia (platelets < 50,000/mm³) that does not resolve to ANC ≥ 500/mm³ and platelets ≥ 50,000/mm³ (transfusion independent) by Day 18 will be considered dose-limiting (See [Section 6.2.1](#)).
- Platelet count < 25,000/mm³ on 2 separate days, or requiring a platelet transfusion on 2 separate days, within a 7 day period
- Myelosuppression that causes a delay of > 14 days between treatment cycles.

- b) Note: Grade 3 or 4 febrile neutropenia will not be considered a dose-limiting toxicity.

6.0 DOSE MODIFICATIONS FOR ADVERSE EVENTS

The Study Chair must be notified of any dosage modification or use of myeloid growth factor.

6.1 Dose Modification for Day 1 Dosing

6.1.1 Dose Modifications for Hematologic Toxicity

6.1.1.1 Patients who have dose-limiting thrombocytopenia should receive subsequent cycles at the next lower dose level.

6.1.1.2 Patients who have dose-limiting neutropenia with no other dose-limiting toxicity should receive the same dose in the next cycle with myeloid growth factor support or receive study drug at the next lower dose level. [Note: Patients MUST NOT receive prophylactic myeloid growth factor in the first cycle of therapy (See [Section 7.4](#)).] If dose-limiting neutropenia recurs after myeloid growth factor is added, then the patient should be given the next lower dose level for subsequent cycles. If dose-limiting neutropenia recurs in a patient that has received a dose level reduction but has not received myeloid growth factor, then myeloid growth factor should be administered. If, per the treating physician, addition of myeloid growth factor is not in the best interest of the patient, the patient should be removed from protocol therapy. In the case where myeloid growth factor is used, it should be initiated 24 hours after the dose. If the day 15 dose is delayed to allow for recovery, the myeloid growth factor should not be given until 24 hours after the day 15 dose is given. If the day 15 dose is omitted, myeloid growth factor can be given at the time the decision is made to omit the dose.

THIS PROTOCOL IS FOR RESEARCH PURPOSES ONLY, SEE PAGE 1 FOR USAGE POLICY

6.1.1.3 Patients who experience dose-limiting thrombocytopenia after one dose reduction or dose-limiting neutropenia after addition of myeloid growth factor and one dose reduction must be removed from protocol therapy.

6.1.1.4 Patients who have a dose-limiting hematological toxicity that does not resolve to eligibility parameters within 21 days after the planned start of the next treatment cycle must be removed from protocol therapy.

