6.1.2 Dose Modifications for Non-Hematological Toxicity

6.1.2.1 Patients who have any dose-limiting non-hematological toxicity (as defined in [Section 5.5.1](#)) may continue on protocol therapy upon meeting eligibility lab requirements or baseline but should receive subsequent doses at the next lower dose level.

6.1.2.2 If the patient experiences non-hematological dose-limiting toxicity after one dose reduction, the patient must be removed from protocol therapy.

6.1.2.3 Patients who have a dose-limiting non-hematological toxicity that does not resolve to baseline or eligibility (whichever is higher) within 21 days after the planned start of the next treatment cycle must be removed from protocol therapy.

6.2 **Dose Modifications for Day 15 Dosing due to Toxicity on Day 15.**

6.2.1 Dose Modifications for Hematological Toxicity:

6.2.1.1 Patients who have Grade 4 neutropenia or Grade 3 thrombocytopenia (platelets < 50,000/mm³) on Day 15 will have their dose withheld. If the toxicity resolves to ANC \geq 500/mm³ and platelets \geq 50,000/mm³ (transfusion independent) by Day 18, the dose may be given. Platelets cannot be given to achieve a platelet count >50,000/mm³ to receive the day 15 dose. If the toxicity does not resolve to ANC \geq 500/mm³ and platelets \geq 50,000/mm³ by Day 18, the dose will be omitted and this will be considered a DLT. Patients who require that their Day 15 dose be omitted for Grade 4 neutropenia or Grade 3 platelets (< 50,000/mm³) after a dose reduction for any reason must be removed from protocol therapy.

6.2.1.2 Patients who meet hematological DLT criteria as defined in [Section 5.5.2](#) on Day 15 will have their Day 15 dose omitted. Patients should receive subsequent cycles of drug per [Section 6.2](#) after their toxicity resolves, no sooner than the planned start of the subsequent cycle. Patients who require that their Day 15 dose be omitted for hematologic DLT as defined in [Section 5.5.1](#) after one dose reduction must be removed from protocol therapy.

6.2.2 Dose Modifications for Non-Hematologic Toxicity:

6.2.2.1 Patients who have Grade 3 or Grade 4 non-hematological toxicity attributable to the study drug prior to the Day 15 dose (with the exception

THIS PROTOCOL IS FOR RESEARCH PURPOSES ONLY, SEE PAGE 1 FOR USAGE POLICY

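### When Grade 4 neutropenia recurs on Day 15 after a dose reduction without growth factor, Section 6.1.1.2 keeps the patient on therapy and Section 6.2.1.1 removes the same patient

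*Combined protocol and SAP*

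**What the plan says.** Section 5.6.2 makes Grade 4 neutropenia on Day 15 a hematological DLT if it has not resolved by Day 18, and refers to Section 6.2.1. Section 6.2.1.1 agrees: "the dose will be omitted and this will be considered a DLT". Two sets of rules then bear on a patient who has already been dose-reduced.

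- **Section 6.1.1.2.** A first neutropenia DLT may be handled by growth factor at the same dose or by the next lower dose level. If the neutropenia recurs in a patient who "has received a dose level reduction but has not received myeloid growth factor, then myeloid growth factor should be administered". The alternative is the physician's judgement: if "addition of myeloid growth factor is not in the best interest of the patient, the patient should be removed from protocol therapy".
- **Section 6.1.1.3.** Removal is mandatory for "dose-limiting neutropenia after addition of myeloid growth factor and one dose reduction must be removed from protocol therapy".
- **Section 6.2.1.1.** "Patients who require that their Day 15 dose be omitted for Grade 4 neutropenia or Grade 3 platelets" below the stated count "after a dose reduction for any reason must be removed from protocol therapy".
- **Section 6.2.1.2.** Removal also follows a Day 15 omission for hematologic DLT after one reduction. The sentence takes its DLT definition from Section 5.5.1, a number that no longer holds one.

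Section 6.1 is headed as covering Day 1 dosing and Section 6.2 as covering Day 15 dosing.

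**The concern.** For the same patient and the same toxicity, one rule calls for growth factor as the alternative to removal, and the other orders removal. Sections 6.1.1.2 and 6.1.1.3 make removal for neutropenia depend on growth factor having been tried or judged unsuitable. Sections 6.2.1.1 and 6.2.1.2 make it depend on the dose reduction alone. Section 10.1(b) refers removal for adverse events to Section 6.0 as a whole, so it does not choose between them.

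Removal ends exposure, and under Section 10.2(a) the patient goes off study 30 days after the last dose. A Part B patient who leaves before the four-month assessment counts as not a disease control success under Section 11.7. The same patient kept on therapy might have been a success.

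**Working it through.** No design figure is involved in the contradiction itself, so the check is a trace of one patient through the text, followed by the arithmetic for its consequences.

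**1. The patient.** A neutropenia DLT occurs in one cycle and is managed by the next lower dose level, without growth factor (allowed by 6.1.1.2). In a later cycle there is Grade 4 neutropenia on Day 15 and ANC is still below 500/mm³ on Day 18.

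| Section | Condition | Met? | Result |
|---|---|---|---|
| 5.6.2 | Day 15 Grade 4 neutropenia unresolved by Day 18 | Yes | DLT |
| 6.1.1.2 | DLT neutropenia recurs, reduced, no growth factor | Yes | Give growth factor; removal only if judged unsuitable |
| 6.1.1.3 | Growth factor and one reduction | No | Removal not triggered |
| 6.2.1.1 | Day 15 omitted, any earlier reduction | Yes | Must be removed |
| 6.2.1.2 | Day 15 omitted for hematologic DLT after one reduction | Yes, if the outdated reference is read as hematologic DLT | Must be removed |

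**2. Do the headings separate the rules?** Section 6.1.1.2 itself deals with omitted Day 15 doses: "If the day 15 dose is omitted, myeloid growth factor can be given at the time the decision is made to omit the dose". The only criterion in 5.6.2 that names neutropenia is the Day 15 one. The Day 1 section therefore reaches this event, and no order of precedence is stated.

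**3. Do the cross-references settle it?** No. Section 6.2.1.2 states "Patients should receive subsequent cycles of drug per" Section 6.2, which is the section it sits in. It cites 5.5.2 and then 5.5.1 for hematologic DLT. Section 5.5 is now adverse event grading, the definitions are in 5.6, and 5.6.1 is the non-hematological list.

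**4. Limits of the conflict.** Neutropenia that is dose-limiting only through a delay of more than 14 days does not trigger the Day 15 sentence in 6.2.1.1. If the earlier reduction was for another toxicity, a first neutropenia DLT is not a recurrence, so the quoted sentence of 6.1.1.2 is not triggered.

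**5. Timing in Part B.** Assume 28-day cycles started on time. Day 1 of cycle k is study day 28(k − 1) + 1. With Day 15 omitted, that is the last dose, and off study falls 30 days later. Four months is about day 122 (4 × 30.4).

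- Cycle 2: last dose day 29, off study day 59.
- Cycle 3: last dose day 57, off study day 87.
- Cycle 4: last dose day 85, off study day 115.

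The Section 8.1 table schedules a Part B scan after cycle 4, near day 4 × 28 = 112. Removal in cycle 2 or 3 precedes it. Removal in cycle 4 leaves that scan inside the study window.

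**6. Frequency.** Section 9.1.8 lists decreased neutrophil count, of any grade, in under 3% of patients. If that carries over to the 29 Part B patients, fewer than 29 × 0.03 = 0.87 patients are expected to have any decrease. The conflict needs a Grade 4 event unresolved by Day 18, after an earlier neutropenia DLT, so the expected number is smaller still.

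**7. Reach into the decision (Section 11.6).** Stage 1 stops with 4 or fewer disease control successes in 19 and 1 or fewer RECIST responders. The final result is negative with 8 or fewer successes in 29 and 4 or fewer responders. One patient's status matters only at 4 versus 5 or 8 versus 9, and only when the responder count also falls short.

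**The case against.** The best reply is that the sentence on omitted Day 15 doses in 6.1.1.2 has a use outside the disputed case. A patient kept at the same dose with growth factor can also have a Day 15 dose omitted. The recurrence sentence would also keep a role in the cycle-delay case if 6.2.1.1 governed every Day 15 omission. So a reading with 6.2 as the specific provision is available. It remains a reading that the site must supply. Each rule is specific in its own way (one to the day, the other to reduction without growth factor), and 6.1.1.3 repeats the condition of 6.1.1.2 without excepting Day 15.

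A second reply is central oversight. The Study Chair must be told of any dose modification or growth factor use (6.0) and should be told before growth factor is started (7.4), and study data are reviewed weekly (14.3). This makes divergent handling across sites less likely, and a reader should not infer that it would go unnoticed. It does not say which rule the Study Chair should apply.

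The third reply is rarity, and it stands. In the adult phase 1 trial the only treatment-related event above Grade 2 was one GGT elevation (2.3.1), and the first six Part A patients had no DLT (2.5).

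Three stronger readings are tempting and are not supported:

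- That all dose-limiting neutropenia after a reduction is affected. Step 4 of the working shows two cases that are not.
- That one such patient could decide the trial. That is true of any threshold rule, and here it also requires the RECIST criterion to fail.
- That removal in any of cycles 2 to 4 costs the patient the four-month assessment. In cycle 4 the scheduled scan still falls before the patient goes off study.

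**Conclusion.** Wrong as written: an internal contradiction, confined to one defined case. For a patient reduced for dose-limiting neutropenia without growth factor, whose Day 15 dose in a later cycle is omitted for Grade 4 neutropenia unresolved by Day 18, 6.1.1.2 and 6.1.1.3 lead to growth factor without mandatory removal, while 6.2.1.1 orders removal. Section 6.2.1.2 points the same way as 6.2.1.1, but through an outdated reference, so less weight rests on it.

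The conclusion about the text needs no assumption beyond the sections cited. The view of its consequences assumes on-time cycles and that the listed incidence carries over to this population. On those assumptions the effect on Part B is small: a possible change of disease control status in a rare patient removed mainly in cycle 2 or 3. The reason to act is that an instruction on stopping treatment cannot be followed as it stands.

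**What to change.** Reconcile 6.1.1.2 and 6.1.1.3 with 6.2.1.1 and 6.2.1.2 so that a single disposition applies to Day 15 dose-limiting neutropenia that recurs after a dose reduction without growth factor. State it in one place and cross-refer from the other. Which disposition stands is for the sponsor to decide; this review takes no position.

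In the same edit, replace the references to Section 6.2 for subsequent-cycle dosing in 6.2.1.2 and 6.2.2.2 with the section that holds those rules. Update the Section 5.5.1 and 5.5.2 references throughout Section 6 to the current DLT definitions in 5.6, checking in each case whether the hematological or the non-hematological list is meant.

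The cost is wording in Section 6 at the next amendment. No new data, procedures or sample size are involved.

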6.1.2 Dose Modifications for Non-Hematological Toxicity

6.1.2.1 Patients who have any dose-limiting non-hematological toxicity (as defined in [Section 5.5.1](#)) may continue on protocol therapy upon meeting eligibility lab requirements or baseline but should receive subsequent doses at the next lower dose level.

6.1.2.2 If the patient experiences non-hematological dose-limiting toxicity after one dose reduction, the patient must be removed from protocol therapy.

6.1.2.3 Patients who have a dose-limiting non-hematological toxicity that does not resolve to baseline or eligibility (whichever is higher) within 21 days after the planned start of the next treatment cycle must be removed from protocol therapy.

6.2 **Dose Modifications for Day 15 Dosing due to Toxicity on Day 15.**

6.2.1 Dose Modifications for Hematological Toxicity:

6.2.1.1 Patients who have Grade 4 neutropenia or Grade 3 thrombocytopenia (platelets < 50,000/mm³) on Day 15 will have their dose withheld. If the toxicity resolves to ANC \geq 500/mm³ and platelets \geq 50,000/mm³ (transfusion independent) by Day 18, the dose may be given. Platelets cannot be given to achieve a platelet count >50,000/mm³ to receive the day 15 dose. If the toxicity does not resolve to ANC \geq 500/mm³ and platelets \geq 50,000/mm³ by Day 18, the dose will be omitted and this will be considered a DLT. Patients who require that their Day 15 dose be omitted for Grade 4 neutropenia or Grade 3 platelets (< 50,000/mm³) after a dose reduction for any reason must be removed from protocol therapy.

6.2.1.2 Patients who meet hematological DLT criteria as defined in [Section 5.5.2](#) on Day 15 will have their Day 15 dose omitted. Patients should receive subsequent cycles of drug per [Section 6.2](#) after their toxicity resolves, no sooner than the planned start of the subsequent cycle. Patients who require that their Day 15 dose be omitted for hematologic DLT as defined in [Section 5.5.1](#) after one dose reduction must be removed from protocol therapy.

6.2.2 Dose Modifications for Non-Hematologic Toxicity:

6.2.2.1 Patients who have Grade 3 or Grade 4 non-hematological toxicity attributable to the study drug prior to the Day 15 dose (with the exception

THIS PROTOCOL IS FOR RESEARCH PURPOSES ONLY, SEE PAGE 1 FOR USAGE POLICY

of the DLT exclusions in [Section 5.5.1](#)) will be considered to have had a DLT. If the toxicity resolves to meet eligibility or \leq Grade 2 (if not part of eligibility criteria) by Day 15, the dose may be given but at the next lower dose level.

6.2.2.2 Patients who have Grade 3 or Grade 4 non-hematological toxicity attributable to the study drug on Day 15 prior to dosing (with the exception of the DLT exclusions in [Section 5.5.2](#)) will have their dose withheld and this will be considered a DLT. If the toxicity resolves to meet eligibility or \leq Grade 2 (if not part of eligibility criteria) by Day 18, the dose may be given but at the next lower dose level. If the toxicity does not resolve by Day 18, the dose will be omitted. Patients should receive subsequent cycles of drug but with dose modifications according to [Section 6.2](#).

6.2.2.3 If the patient experiences non-hematological dose-limiting toxicity after one dose reduction, the patient must be removed from protocol therapy.

6.2.3 Dose Modifications for Infusion-Related Reactions:

For patients who have allergic or acute infusion reactions to VX15/2503, therapy modifications based on grade should be as follows

Grade (CTCAE v.5) Infusion Related Reaction	Action
Grade 1 Transient flushing or rash, drug fever < 38° C	
 • Monitor patient until recovery from symptoms; infusion rate may be slowed. • If the infusion is interrupted, then restart the infusion at 50% of the original infusion rate when symptoms resolve. Monitor patient closely. 
The following prophylactic premedications are recommended: diphenhydramine 1 mg/kg with max 50 mg (or equivalent) and/or acetaminophen 10-15 mg/kg (max 1000 mg) at least 30 minutes before additional VX15/2503 administrations, slowing infusion rate as above. Note: Prophylactic premedications should be administered upon restart of infusion, when symptoms resolve.

Grade 2 Rash, flushing, urticaria, dyspnea, drug fever \geq 38°C	
 • Stop infusion, begin an IV infusion of normal saline, and treat the subject with diphenhydramine 1 mg/kg with max 50 mg IV (or equivalent) and/or acetaminophen 10-15 mg/kg (max 1000 mg); remain at bedside and monitor patient until resolution of symptoms. Corticosteroid or bronchodilator therapy may also be administered as appropriate. • If the infusion is interrupted, then restart the infusion at 50% of the original infusion rate when symptoms resolve. Monitor patient closely. • If symptoms recur, then no further VX15/2503 will be administered at that visit. Administer diphenhydramine 1 mg/kg with max 50 mg IV (or equivalent), and remain at

THIS PROTOCOL IS FOR RESEARCH PURPOSES ONLY, SEE PAGE 1 FOR USAGE POLICY

	
bedside and monitor the patient until resolution of symptoms.
 
The following prophylactic premedications are recommended: diphenhydramine 1 mg/kg with max 50 mg IV (or equivalent) and acetaminophen (10-15 mg/kg, max 1000 mg) should be administered at least 30 minutes before additional VX15/2503 administrations. If clinically indicated, corticosteroids (recommended dose: 1-2 mg/kg/day methylprednisolone IV or equivalent) may be used.


Grade 3 or 4 Symptomatic bronchospasm with or without urticaria, allergy-related edema/angioedema, hypotension; Anaphylaxis
	
 • Immediately discontinue infusion of VX15/2503. • Begin an IV infusion of normal saline, and treat the subject as follows. Recommend bronchodilators, epinephrine 0.2 to 1 mg of a 1 mg/ml solution for subcutaneous administration, 0.1 to 0.25 mg of a 0.1 mg/ml solution injected slowly for IV administration, 0.01 mg/kg of 1:1000 dilution (0.01 ml/kg/dose) for intramuscular administration, and/or diphenhydramine 1 mg/kg with max 50 mg IV with 1-2 mg/kg/day methylprednisolone IV (or equivalent), as needed. • Patient should be monitored until the investigator is comfortable that the symptoms will not recur. • VX15/2503 will be permanently discontinued. 
Investigators should follow their institutional guidelines for the treatment of anaphylaxis. Remain at bedside and monitor patient until recovery from symptoms. In the case of late-occurring hypersensitivity symptoms (e.g., appearance of a localized or generalized pruritis within 1 week after treatment), symptomatic treatment may be given (e.g., oral antihistamine, or corticosteroids).

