4.1.7 Organ Function Requirements

4.1.7.1 Adequate Bone Marrow Function Defined as:

- a. For patients with solid tumors without known bone marrow involvement:
 - Peripheral absolute neutrophil count (ANC) $\geq 1000/\text{mm}^3$
 - Platelet count $\geq 100,000/\text{mm}^3$ (transfusion independent, defined as not receiving platelet transfusions for at least 7 days prior to enrollment)
 - Hemoglobin ≥ 8.0 g/dL at baseline (may receive RBC transfusions)

- b. Patients with known bone marrow metastatic disease will be eligible for study provided they meet the blood counts in 4.1.7.1.a (may receive transfusions provided they are not known to be refractory to red cell or platelet transfusions). These patients will not be evaluable for hematologic toxicity. At least 5 of every cohort of 6 patients must be evaluable for hematologic toxicity for the dose-confirmation part of the study. If dose-limiting hematologic toxicity is observed, all subsequent patients enrolled must be evaluable for hematologic toxicity.

4.1.7.2 Adequate Renal Function Defined as:

- Creatinine clearance or radioisotope GFR $\geq 70\text{ml}/\text{min}/1.73 \text{ m}^2$ or
- A serum creatinine based on age/gender as follows:

Age	Maximum Serum Creatinine (mg/dL)	
	Male	Female
1 to < 2 years	0.6	0.6
2 to < 6 years	0.8	0.8
6 to < 10 years	1	1
10 to < 13 years	1.2	1.2
13 to < 16 years	1.5	1.4
≥ 16 years	1.7	1.4

The threshold creatinine values in this Table were derived from the Schwartz formula for estimating GFR (Schwartz et al. J. Peds, 106:522, 1985) utilizing child length and stature data published by the CDC.

4.1.7.3 Adequate Liver Function Defined as:

- Bilirubin (sum of conjugated + unconjugated) ≤ 1.5 x upper limit of normal (ULN) for age
- (ALT) (SPGT) ≤ 135 U/L. For the purpose of this study, the ULN for ALT is 45 U/L.
- Serum albumin ≥ 2 g/dL.

THIS PROTOCOL IS FOR RESEARCH PURPOSES ONLY, SEE PAGE 1 FOR USAGE POLICY

4.1.7.4 Adequate Pulmonary Function Defined as:

- a. No clinical indications such as evidence of dyspnea at rest, or exercise intolerance due to pulmonary insufficiency.
- b. If clinical indications, pulse oximetry >94% on room air.

4.1.8 **Informed Consent:** All patients and/or their parents or legally authorized representatives must sign a written informed consent. Assent, when appropriate, will be obtained according to institutional guidelines.

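### Section 6.2.1.1 calls every Day 15 dose omitted for unrecovered counts a DLT, without the attribution and evaluability limits of Sections 5.6 and 5.6.2: a minor inconsistency that one clause corrects

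*Combined protocol and SAP*

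**What the plan says.** **The definition.** Section 5.6 states: "DLT will be defined as any of the following events that are possibly, probably or definitely attributable to protocol therapy". Section 5.6.2 opens its hematological criteria with "In patients evaluable for hematological toxicity". The first of these is the Day 15 criterion: Grade 4 neutropenia or platelets below 50,000/mm³, not recovered by Day 18. It cross-refers to 6.2.1. For patients with known marrow metastases, Section 4.1.7.1.b says: "These patients will not be evaluable for hematologic toxicity".

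**The dosing rule.** Section 6.2.1.1 applies the same Day 15 and Day 18 thresholds to any patient with the cytopenia and concludes: "by Day 18, the dose will be omitted and this will be considered a DLT". It mentions neither attribution nor evaluability. The parallel rule in 6.2.2.2 is limited to "non-hematological toxicity attributable to the study drug on Day 15 prior to dosing", and 6.2.2.1 also requires attribution.

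**What follows from the label.** Section 6.1.1.1 sends dose-limiting thrombocytopenia to the next lower dose level, which is 10 mg/kg (5.3.1). Section 6.1.1.2 lets dose-limiting neutropenia continue at the same dose with growth factor, or at the lower level. Section 6.2.1.1 adds that a patient whose Day 15 dose is omitted "after a dose reduction for any reason must be removed from protocol therapy".

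**The concern.** The same event has two different statuses. Under 5.6.2 an unrecovered cytopenia in a marrow-metastatic patient is not a DLT. Under 6.2.1.1 it is.

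The conflict can arise with no drug effect. Section 4.1.7.1.b says marrow patients "may receive transfusions provided they are not known to be refractory to red cell or platelet transfusions" in meeting the entry counts. On Day 15, 6.2.1.1 requires transfusion-independent platelets and says: "Platelets cannot be given to achieve a platelet count" above the threshold. A transfusion-supported patient can therefore qualify at entry and fail on Day 15 because of the disease.

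The main stake is that patient's treatment: a dose reduction, and possibly removal, that the DLT definition does not call for. The second stake is the DLT counts. The likeliest setting is the PK expansion cohort, which 11.1 opens without a heme-evaluability restriction and whose DLTs count toward the MTD limit (11.2.2). DLTs in Part A patients at the RP2D also enter the running suspension rule of 11.6.

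**Working it through.** **Step 1: follow one patient.** Take a marrow-metastatic patient at 20 mg/kg with disease-related platelets below 50,000/mm³ on Day 15, not recovered by Day 18.

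| Event | 6.2.1.1 read literally | 5.6, 5.6.2 and 4.1.7.1.b |
|---|---|---|
| First omission | DLT | Not a DLT: not attributable, patient not evaluable |
| Next cycle | 10 mg/kg (6.1.1.1) | No DLT-driven reduction; restart needs the 5.2 criteria |
| Second omission | After a reduction, so removal | No earlier reduction from this cause, so that removal rule is not met |

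For neutropenia alone the literal reading does not force a reduction, because 6.1.1.2 offers the same dose with growth factor.

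**Step 2: effect on the DLT counts.** The plan states no operating characteristics for these rules, so there is no figure to reproduce. From the documents:

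- 0 DLTs in the first 6 Part A patients (2.5);
- up to 6 PK expansion patients (11.1);
- MTD exceeded if at least one third of the combined cohort has a DLT (11.2.2), so 12/3 = 4 of 12;
- Part B enrollment suspended if 2 or more of the first 6 adults have a Cycle 1 DLT (11.6);
- study suspended if the running percentage is above 33% (11.6).

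Assumptions not in the documents: a true DLT rate p of 0.05, range 0.02 to 0.10, and exactly one mislabelled Cycle 1 event that review did not correct.

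*2 of 6 adults.* With no mislabel, P(X ≥ 2 of 6) = 1 − (1−p)⁶ − 6p(1−p)⁵. At p = 0.05 this is 1 − 0.7351 − 0.2321 = 0.0328. With one mislabel, one more among the other five is enough: 1 − (1−p)⁵ = 1 − 0.7738 = 0.2262.

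*MTD limit, 4 of 12 after 0 of 6.* With no mislabel, P(X ≥ 4 of 6) = 0.000086 at p = 0.05. With one, P(X ≥ 3 of the other 5) = 0.00116.

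*Running rule.* Start from 0 of 6, add 12 patients (6 PK and 6 adults), and check after each. Part A patients at the RP2D are assumed to be in the denominator. With 33.3% counted as above 33%, the stopping count is 3 at 7–9 patients, 4 at 10–12, 5 at 13–15 and 6 at 16–18. The mislabel is placed first, the order with the most impact.

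| Rule | p = 0.02 | p = 0.05 | p = 0.10 |
|---|---|---|---|
| MTD limit, 4 of 12 | 0.000002 → 0.00008 | 0.00009 → 0.0012 | 0.0013 → 0.0086 |
| Running >33% | 0.00001 → 0.0005 | 0.0002 → 0.0035 | 0.0027 → 0.019 |
| 2 of 6 adults | 0.006 → 0.10 | 0.033 → 0.23 | 0.11 → 0.41 |

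The last row applies only if a marrow-involved osteosarcoma adult is among the first six. All rows are conditional on the mislabel having happened. They are not estimates of how often it would.

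**The case against.** The strongest reply is that the definition governs. Section 5.6 says what a DLT is. Section 5.6.2 states the same Day 15 criterion for evaluable patients only and points to 6.2.1 as its counterpart. Section 6.1.1.1, which actually cuts the dose, uses the defined term. Section 11.2.2 points the MTD count to the definition section, though under 5.5, which is now adverse event grading. This largely stands: the intended rule is clear. It does not remove the conflict for a site deciding between Day 15 and Day 18, because 6.2.1.1 has no pointer to the definition and nothing expressly overrides it. The counts in 11.6 carry no pointer either.

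There are also safeguards. Section 6.0 requires the study chair to be told of any dose modification. Under 14.3 the chair records evaluability and DLTs, with weekly review. Notification is not approval, but an uncorrected mislabel becomes less likely.

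Harm from the lower dose is not shown. The dose rationale in 2.5 says modeling suggests that 10 mg/kg maintains T-cell saturation and may be active. Removal needs two omissions. Section 9.1.8 lists decreased neutrophil count as rare and does not list thrombocytopenia, although the scenario here is disease-related and does not depend on drug toxicity.

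A reader might infer that the 20 mg/kg RP2D is in doubt. The documents do not support that: dose confirmation ended with 0 DLTs in 6. A reader might also take the 0.03 to 0.23 change as the size of the problem. It is conditional on a particular patient and an uncorrected error, and it leads to suspension pending committee discussion, not termination.

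**Conclusion.** The inconsistency is real and should be corrected, but it is minor. It is an inconsistent rule, not a design flaw, since 5.6 and 5.6.2 already state the intended design. The consequence falls mainly on the individual marrow-metastatic patient with thrombocytopenia: 20 to 10 mg/kg after one omission and removal after a second, if 6.2.1.1 is followed to the letter.

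The effect on the MTD is negligible: at most 0.0086 at an assumed 10% DLT rate, even given a mislabel. The effect on the running 33% rule is small. The 2-of-6 adult rule is more sensitive, but only in the narrow case described.

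The documents give neither the share of patients with marrow disease nor the rate of unrecovered Day 15 cytopenias, so no overall frequency can be given. They do not show that any patient has been mislabelled.

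**What to change.** In 6.2.1.1, replace the clause on unrecovered counts with: *the dose will be omitted, and this will be considered a DLT only if it meets Sections 5.6 and 5.6.2 (at least possibly attributable to protocol therapy, in a patient evaluable for hematological toxicity)*. Keep the hold, omission, transfusion and removal rules for all patients.

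This clause is sufficient. If the protocol team also wants to state what follows an omission that is not a DLT, it should not impose an automatic dose reduction. That would treat a non-DLT neutropenia more strictly than 6.1.1.2 treats a true one. Instead:

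- if the cytopenia is judged at least possibly drug-related, apply the existing 6.1.1 options, including the same dose with growth factor for neutropenia, and the 21-day limit in 6.1.1.4;
- otherwise, resume at the same dose when the 5.2 criteria are met.

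Stating this would also keep the growth-factor route open, since 7.4 ties it to 6.1.1.2, which is written for dose-limiting neutropenia.

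The cost is one clause, with no added patients, tests or visits. The downside is that a drug-related cytopenia in a patient with marrow disease is not counted as a DLT, which 5.6.2 already accepts.
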